## D. RESEARCH APPROACH

**D.1. General Overview and Design (see figure):** Our research design is predicated on the notion that patient screening would appropriately identify a more targeted group for referral for appropriate diagnostic services. We will conduct three complementary studies to evaluate the effectiveness of the PDM, the QDRS or the combined (PDM + QDRS) approaches for early detection of ADRD. These approaches will be embedded within the EHR systems of diverse rural, suburban, and urban primary care practices in central Indiana and south Florida. The first study will be a clinical validation study (stage III) of the three approaches; the PDM, the QDRS, and the combination of both (the PDM + QDRS). The approaches will be clinically validated in real-world and diverse clinical settings in comparison to the gold standard of ADRD diagnosis used in the NIA-funded ADRD Research Centers across the nation. The gold-standard evaluations will allow us to determine the accuracy of the screening approaches and compare their performances. The other studies will be two independent pragmatic cluster-randomized controlled comparative effectiveness trials (phase IV) of the approaches embedded within the AWV (PDM within AWV, PDM + QDRS within the AWV) in comparison to the current AWV only process (AWV without PDM or QDRS). The two trials will be conducted in two separate healthcare systems; the first trial will be conducted at Eskenazi Health and within 12 months a second replicated trial will be conducted at University of Miami Health. Both trials will have identical methodology and would compare the performance of the three approaches in increasing the incidence rate of new ADRD subsequently documented in the EHR by the primary care practices.

**D.2. Clinical Setting for both the Clinical Validation Study and the Pragmatic Cluster-Randomized Controlled Comparative Effectiveness Trials:** All studies will be conducted in diverse rural, suburban, and urban primary care practices in central Indiana and south Florida. Such primary care practices include 10 federally qualified health centers affiliated with Eskenazi Health in Indianapolis and 10 primary care practices in South Florida affiliated with University of Miami (UHealth). Eskenazi Health is one of the largest safety net integrated healthcare systems in the nation serving underprivileged older residents of Marion County including African Americans (50%) and dual eligible Medicaid and Medicare

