**D.5. Interventions and Control for the Pragmatic (Phase IV) Trials:** Our interdisciplinary scientific teams developed and tested both the PDM and the QDRS. Drs. [name] and [name] leveraged the widely available EHR data and the advantage of ML to develop the PDM with an approximate 80% accuracy for one-year and three-year prediction horizons. [name] team developed and tested the QDRS as a practical 2-3 minute patient reported outcome (PRO) tool for both early detection and staging of ADRD. Each pragmatic trial will randomize primary care practices into one of three approaches for early detection of ADRD at (1:1:1) ratio. These approaches include the current state of using AWV in primary care (the control group), the incorporation of the PDM into the AWV, and the combination of PDM and QDRS (Passive + QDRS). All of the three approaches will be implemented within the current Medicare funded AWV and will be integrated within the provider clinical encounter to accommodate the clinical flow and data capture and results display needs of the primary care practices. To randomly assign each practice to one of the three screening approaches, we will use a computer-generated randomization scheme.

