Because the other studies are two separate pragmatic clinical trials, participants will be cluster-randomized to three different arms. This approach ensures that rigorous testing of the outcomes (incident ADRD detection and acceptance of subsequent diagnostic assessments) is not contaminated by the other screening approaches in other arms of interest. In addition, the 400 patients in study 1 will be excluded from the two pragmatic trials to avoid contamination. The total sample for each pragmatic trial will be slightly over 2,600, if each of enrolled practice screen conservatively 175 patients per year for a total of two years of screening. Alternatively, the total sample size for each trial will be 3,600, if we recruit, as we have in past trials, 200 patients per clinic. The table below shows the power for comparing ADRD incidence and acceptance rates between two different arms under the conservative and historical recruitment scenarios. Calculations were based on using nonlinear mixed models to compare two independent proportions, assuming cluster randomization (i.e., level-2 randomization) and the

ICC is 0.01. The “AWV alone” arm is expected to have ADRD incidence of 6% and acceptance rate of 44%. The table shows that power will exceed 80% to detect ADRD incidence of 6% vs 13%, even under conservative recruitment projections, and power for comparing acceptance rates will be 99%.

Outcome	Conservative recruitment* (N = 2,600)	Projected (feasible historically) recruitment* (N = 3,600)
ADRD incidence 6% vs 13%	86%	89%
Acceptance 44% vs 66%	99%	99%

\*Conservative recruitment = Total of 2,600 patients with 866 patients and 5 clusters per each of 3 arms; power for pairwise comparisons based on 1,732 patients with 866 patients and 5 clusters per each of 2 arms, and M = 173.2 patients per cluster. Historical recruitment = Total of 3,600 patients with 1,200 patients and 5 clusters per each of 3 arms; power for pairwise comparisons based on 2,400 patients with 1,200 patients and 5 clusters per each of 2 arms, and M = 240 patients per cluster.

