
#### **D.10. Timetable & Project Administration.**

We are proposing a 5-year grant period to accommodate recruitment, management of multiple data sources, primary data collection, training data collection staff, and multiple distinct analytic techniques. During the first six months, we will hire and train our research team, set up the organizational structure of the research projects, and finalize IRB approval. In the following 18 months, we will deploy the PDM and the QDRS into the Epic EHR environments in the two health care systems in Indiana (Eskenazi Health) and Florida (UHealth). Also by the end of Year 2, we will recruit 400 subjects into our first clinical validation (Stage III) study and complete the data collection for Aim 1. In Year 3, we will complete the data analysis and the dissemination activities related to Primary and Secondary Aim 1. In the beginning of Year 3, we will recruit the 15 primary care practices from the two sites into our pragmatic cluster-randomized controlled comparative effectiveness (phase IV) trials. In Year 4 we will retrieve the data related to Primary Aim 2 from the Datawarehouse of the Epic EHR systems at both participating healthcare systems (Eskenazi Health and UHealth) and complete data analysis for Primary and Secondary Aim 2. In Year 5, we will share our de-identified data with the scientific community and disseminate the result of our trial to the scientific community via peer reviewed publication and presentation at national and international scientific conferences. In the same year, we will share our codes for both the PDM and the QDRS with Epic headquarters to make sure that these codes are available for any healthcare system with Epic across the country. We will also share technical details in a platform-agnostic manner to aid implementation in other EHR platforms.

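### The Aim 2 power figures need 15 practices in each trial, but the protocol lists 10 per health system and plans to recruit 15 across both

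*Combined protocol and SAP*

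**What the plan says.** D.8.c sizes each pragmatic trial separately. The conservative scenario is "Total of 2,600 patients with 866 patients and 5 clusters per each of 3 arms", with 173.2 patients per practice. The second scenario has 3,600 patients, again with 5 practices in each of 3 arms, and 240 patients per practice. The stated power for incidence is 86% and 89%, and the text concludes that "power will exceed 80% to detect ADRD incidence of 6% vs 13%, even under conservative recruitment projections".

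Other sections give different practice counts:

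- D.1: "The two trials will be conducted in two separate healthcare systems". The trials are called independent, and the second replicates the first.
- D.2: the practices include "10 federally qualified health centers affiliated with Eskenazi Health in Indianapolis and 10 primary care practices in South Florida".
- D.5: "Each pragmatic trial will randomize primary care practices into one of three approaches for early detection of ADRD at (1:1:1) ratio".
- D.10: "we will recruit the 15 primary care practices from the two sites".

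On patient numbers, D.8.c explains the conservative total by "175 patients per year for a total of two years of screening" per practice. For the larger total it says that "the total sample size for each trial will be 3,600, if we recruit, as we have in past trials, 200 patients per clinic".

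**The concern.** Three practice counts stand side by side: 30 (two trials of 15, D.8.c), 20 (10 per system, D.2) and 15 (both sites, D.10). They cannot all be the number randomized. Ten practices cannot be split 5/5/5. They give 3/3/4, or 3/3/3 with one unused. Fifteen practices over two trials leave 7 or 8 per trial if shared about evenly, so 2 or 3 per arm.

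In a cluster-randomized trial the number of clusters largely fixes the power, and extra patients within a practice bring diminishing returns. Incidence is the primary outcome of both trials. If each trial really has 7 to 10 practices, the plan overstates the chance that either one detects the hypothesized effect. A null result in one system, or a failure to replicate, could then be read as absence of effect when low power is a sufficient explanation.

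**Working it through.** **Inputs.** Two-sided alpha 0.05, ICC 0.01, incidence 6% versus 13% and the cluster sizes all come from D.8.c. The inflation factor 1 + (M − 1) × ICC is given there for Aim 1 and is applied here to Aim 2.

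**Formulas.** For k practices of M patients in an arm, effective n = kM / [1 + (M − 1) × 0.01]. With d = 0.07:

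- unpooled power = Φ(d/SE − 1.96)
- pooled power = Φ((d − 1.96 × SE0)/SE)

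SE uses the two arm-specific variances, and SE0 uses the common proportion.

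**Reproducing the table (5 versus 5).**

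- M = 173.2: inflation 1 + 172.2 × 0.01 = 2.722; effective n = 866/2.722 = 318.1 per arm; power 85.8% unpooled, 85.5% pooled. Stated: 86%.
- M = 240: inflation 3.39; effective n = 1,200/3.39 = 354.0 per arm; power 89.2% unpooled, 89.0% pooled. Stated: 89%.

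The table is therefore correct for five practices per arm.

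**Changing only the practice count** (control versus combined arm; unpooled / pooled power, %):

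| Practices | M = 175 | M = 350 | M = 400 |
|---|---|---|---|
| 3 v 3 | 65.3 / 64.8 | 73.9 / 73.4 | 75.1 / 74.6 |
| 3 v 4 | 73.2 / 69.4 | 81.3 / 78.2 | 82.3 / 79.4 |
| 4 v 3 | 69.1 / 71.8 | 77.5 / 79.8 | 78.6 / 80.8 |
| 2 v 2 | 48.5 / 47.9 | 56.5 / 55.9 | 57.6 / 57.1 |

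M = 350 is 175 per year for two years, and M = 400 is 200 per year for two years.

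- Ten practices per trial (3/3/4): 65-73% at M = 175, 73-81% at 350, 75-82% at 400.
- Fifteen over both trials (2 v 2 up to 3 v 3): 48-65%, 56-74% and 57-75%.
- At the table's own M = 173.2, the best case among these is 73.0% (3 v 4, unpooled).

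**Keeping the table's patients per arm on 3 practices.** 866 per arm (M = 288.7) gives 71.9 / 71.5%, and 1,200 per arm (M = 400) gives 75.1 / 74.6%.

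**Ceiling.** As M grows, effective n tends to k/0.01. For 3 v 3 that is 300 per arm and power of at most 83.8 / 83.4%. For 3 v 4 or 4 v 3 the limit is 86.8-89.7%, approached only with very large practice samples.

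**Patient totals.**

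- 15 × 175 = 2,625 matches the conservative total, but two years at 175 would be 15 × 350 = 5,250. The total also equals 7.5 × 350.
- 15 × 200 = 3,000, not 3,600. The larger total equals 15 × 240 or 9 × 400.

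So the text does not settle which number is off.

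**The case against.** - **D.2 is a description of the setting.** It covers the validation study as well, and it says the practices include 10 and 10, so it sets no ceiling. That is fair. Still, no section gives a larger number for either system.
- **The 15 practices in D.10, analysed together, would give exactly 5 per arm and the table's power.** D.8.b describes the models without saying that they are fitted separately by trial. This is the best reading in the plan's favour. It conflicts with the per-trial totals in D.8.c, with the two independent trials in D.1 and with the randomization within each trial in D.5. Reading the 15 as 15 per site would fit D.8.c, but no section lists that many in either system.
- **Larger practice samples help.** Some 3 v 4 and 4 v 3 comparisons reach 80-82% at 350-400 patients per practice. That stands, but these are not the conservative numbers in the table, and none reaches 86%.
- **The figures for 15 practices assume a roughly even split between the trials.** D.10 does not state one. This also stands.
- **Acceptance power may be less secure than it looks.** It stays at about 99% with 3 or 4 practices per arm if every patient counts, as the table assumes. D.8.b defines acceptance among patients who screen positive, and the documents give no screen-positive rate. If 10-30% screened positive in both arms (an assumption), 3 v 3 at M = 173.2 would give about 55-90%, and 5 v 5 about 78-99%. This is separate from the practice count.

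**Conclusion.** The concern holds. The power calculation is right for 15 practices per trial, but no section shows 15 practices in either health system, and two sections point to fewer. On the counts given, incidence power at about 175 patients per practice is 65-73% (10 per trial) or 48-65% (15 over both trials, shared about evenly), against the stated 86%. These figures use the plan's ICC of 0.01, its 6% and 13% rates, equal practice sizes and the large-sample normal test that reproduces the table.

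As a separate sensitivity check, a small-sample t reference lowers everything, including the planned design: 5 v 5 falls to 79.5% and 83.5% with 12 df, and 10 practices give about 53-70% with 7 df. The plan specifies no degrees of freedom, so the conclusion does not rest on this.

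**What to change.** 1. State one number of practices per trial, with its split across the three arms, in the same terms in D.2, D.8.c and D.10. If 15 per trial is intended, show that each system can supply them.
2. Reconcile the patient numbers in D.8.c: 175 per year for two years against 2,600 and 173.2 per practice, and 200 per clinic against 3,600 and 240 per practice.
3. Restate the power table for the confirmed count and name the formula. State the denominator used for acceptance.
4. If a single trial falls below 80% for incidence, say so, and report each trial's between-arm difference with its confidence interval. D.8.b currently promises intervals only for the rate in each arm.
5. Optionally, pre-specify a combined analysis of both trials with health system as a fixed effect. With 20 practices (6 v 6 to 6 v 7, 175-350 patients per practice, t with 16 df) power would be about 88-95%, provided the effect is common to both systems.

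The cost is protocol and SAP wording and, if the count is below 15 per trial, a less favourable power figure. No extra patients are needed, and the optional analysis adds one model.

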#### **D. 9. Potential problems & alternative strategies**

First, while we expect that adding EHR-based data (the PDM) elements to the QDRS based process of ADRD detection will boost validity from 75% to 85% for AUC or for the overall % accuracy of classification, these gains may be marginal (<10%). Smaller gains would signal a precautionary lesson on the limits of EHRs to detect ADRD as currently designed. Second, given the heterogeneity of EHR data, adding EHR data might actually cause the ADRD detection process to gain validity at the cost of reliability. Given Medicare's growing reliance on EHRs for quality measurement, illuminating such a trade-off would be highly policy-relevant. Third, this work involves two states (Florida and Indiana), which may limit generalizability. However, the diversity of the study population may overcome these limitations. Fourth, the intervention faces barriers, such as stakeholder buy-in, unintended consequences, alert fatigue, and clinical uncertainty. We will overcome these barriers by (1) working closely with the leadership of the primary care practices to ensure stakeholder buy in, (2) leverage the trusted relationship between the patient and her primary care team, (3) the proposed PDM and QDRS will be fully integrated within the AWV and the clinical flow of the primary care practices, and (4) working with Drs. [name] and [name] (their Epic Team) to trouble shoot EHR integration barriers and minimize alert fatigue. Based on our extensive preliminary studies, the combined approach of using the PDM and the QDRS would outperform the current state of using the AWV alone or the integration of the PDM within the AWV clinical flow. Fifth, seamlessly integrating the PDM and QDRS within the AWV clinical workflow with limited disruption can be challenging. The Regenstrief Institute has more than a decade of experience with, and has the technical infrastructure in place for, developing and integrating various CDS within Epic, Cerner, and other EHR vendors across the world (see Facilities & Other Resources). We have also allocated sufficient time between the analysis of Aim 1 and go-live of Aim 2 (see **Timetable**) to make any necessary adjustments. Lastly, we will be monitoring uptake and usage of the CDS intervention using the system logs. If uptake during the go-live period appears problematic, we will be able to revisit training / socializing the new workflow with clinical staff or alter the user interface based on feedback.

#### **D.10. Timetable & Project Administration.**

We are proposing a 5-year grant period to accommodate recruitment, management of multiple data sources, primary data collection, training data collection staff, and multiple distinct analytic techniques. During the first six months, we will hire and train our research team, set up the organizational structure of the research projects, and finalize IRB approval. In the following 18 months, we will deploy the PDM and the QDRS into the Epic EHR environments in the two health care systems in Indiana (Eskenazi Health) and Florida (UHealth). Also by the end of Year 2, we will recruit 400 subjects into our first clinical validation (Stage III) study and complete the data collection for Aim 1. In Year 3, we will complete the data analysis and the dissemination activities related to Primary and Secondary Aim 1. In the beginning of Year 3, we will recruit the 15 primary care practices from the two sites into our pragmatic cluster-randomized controlled comparative effectiveness (phase IV) trials. In Year 4 we will retrieve the data related to Primary Aim 2 from the Datawarehouse of the Epic EHR systems at both participating healthcare systems (Eskenazi Health and UHealth) and complete data analysis for Primary and Secondary Aim 2. In Year 5, we will share our de-identified data with the scientific community and disseminate the result of our trial to the scientific community via peer reviewed publication and presentation at national and international scientific conferences. In the same year, we will share our codes for both the PDM and the QDRS with Epic headquarters to make sure that these codes are available for any healthcare system with Epic across the country. We will also share technical details in a platform-agnostic manner to aid implementation in other EHR platforms.

#### Timetable

Project Year	1				2				3				4				5			
Project Quarter	1	2	3	4	1	2	3	4	1	2	3	4	1	2	3	4	1	2	3	4
Study start up	X	X																		
Deploy PDM* + QDRS** tools	X	X	X	X	X	X	X	X												
Clinical Validation (stage III) Study																				
Recruit subjects		X	X		X	X	X	X												
Data Collection (Aim 1)		X	X		X	X	X	X												
Data Analyses (Aim 1)									X	X										
Dissemination (Aim 1)											X	X								
Pragmatic cluster-randomized controlled comparative effectiveness trials (phase IV)																				
Recruit Clinics									X	X	X	X	X	X	X	X				
Data Retrieval from Epic (Aim 2)																		X	X	
Data Analysis (Aim 2)																		X	X	
Sharing Codes																		X	X	X
Sharing De-identified Data (Aim 2)																		X	X	X
Dissemination (Aim 2)																		X	X	X

\*PDM: Passive Digital Marker; QDRS: Quick Dementia Rating Scale.

## E. PROTECTION OF HUMAN SUBJECTS

### Risk to Subjects

Human subjects' involvement and characteristics: Our Digital Detection of Dementia (D) project include the execution of three complimentary studies; the Clinical Validation (stage III) Study and the two Pragmatic cluster-randomized controlled comparative effectiveness (phase IV) trials. These studies will include community-dwelling men and women aged 65 years and older, who receive primary care services within Eskenazi Health located in central Indiana and UHealth in south Florida. They will be English or Spanish speaking, have had at least one visit to primary care practice within past year with available electronic health record (EHR) data from at least three years. The aims of the first Clinical Validation (Stage III) study require a face-to-face or telephone interview and EHR review, to evaluate the accuracy of two scalable approaches for early detection of Alzheimer's disease and related dementias (ADRD); the Passive Digital Marker (PDM) and the Quick Dementia Rating Scale (QDRS). These approaches will be embedded within the EHR systems of diverse rural, suburban, and urban primary care practices in central Indiana and south Florida. Older adult patients represent a somewhat vulnerable group. Our research specifically targets this group in an attempt to enhance the current standard of early detection of ADRD and improve Health for these individuals.

Participants in the first Clinical Validation Study will be informed of the purpose of the overall all goal of Digital Detection of Dementia (D) project of using scalable screening approached to improve the early detection of ADRD in primary care practices) and the procedures related to the clinical Validation study. Signed informed consent will be obtained from these participants. For the clinical validation study, and once informed consent is given, the research team will conduct a gold-standard ADRD assessments (within 30 days of screening) on all patients screened by the PDM and the QDRS.

Sources of material: We will collect EHR data from all patients enrolled in the Clinical Validation study (identified data after obtaining informed consent from subjects) and from patients receiving care in all of the practices enrolled in the Pragmatic cluster-randomized controlled comparative effectiveness (phase IV) trials (de-identified data after obtaining consent from the practice leadership and receiving waiver from the IRB as the two pragmatic trials are Quality improvement trials). For the clinical validation study, the research team will conduct a gold-standard ADRD assessments on all patients screened by the Passive Digital Marker and the Quick Dementia Rating Scale. Such ADRD assessment will be performed face-to-face at research centers in Indianapolis and Miami. To accommodate subject preference and current COVID-19 related safety, the ADRD assessment may be conducted via Zoom or at the subject's home. We have used such assessments for more than a decade with excellent quality assurance and completion. The ADRD assessment will be entered into a Redcap database.

Potential risks: No experimental pharmacological or nonpharmacological intervention will be used in this study. All patients enrolled in the clinical validation study will receive screening for ADRD to validate the accuracy of the PDM and the QDRS. Although data from this study will not be gathered from the patient without his or her consent, it is possible that some of the questions related to ADRD screening and management asked of the respondents could cause anxiety. However, in our recent published ADRD screening trial that evaluated the potential benefits and harms of ADRD screening, there were no differences between the screened and the control group in quality of life, depressive symptoms or anxiety. Furthermore, we anticipate early detection of ADRD in some patients enrolled in the clinical validation study, and up to 13% of patients receiving care in all of the practices enrolled in the pragmatic trials who undergo the screening process and/or the subsequent diagnostic assessment. The impact of this early diagnosis on their quality of life and care was assessed in our recent published trial and found no negative impact on quality of life, depression, anxiety, healthcare utilization or independence

at home. However, it is not known about other potential harms such as stigma. On the other hand, early detection of ADRD is considered part of the standard of care and screening for ADRD is part of the Annual Wellness Visit covered by Medicare. Such early detection would lead to receive appropriate and valuable care both pharmacologically and non-pharmacologically. Such treatment would decrease the patient's disability resulting from unrecognized or unmanaged ADRD and enhance the patients' adherence of medical management of other health conditions. The research personnel will be trained to recognize and minimize any potential discomfort and patients may discontinue participation at any time. If a respondent becomes anxious or upset, the local principal investigator will be notified to intervene. Loss of confidentiality is also a risk in this type of data collection. Our data management and quality assurance technique has proven effective in past trials in maintaining confidentiality, and all study personnel have completed training in Human Subjects Research and HIPAA standards.

In addition, there may be the following possible risks due to blood draw:

- Pain while blood is being drawn
- Bruising of skin on the area after blood draw
- Bleeding after blood draw may occur
- There may be other risks associated with blood draw which may not be known

